12.2.4. Overall Study Sample Size Rationale

The effectiveness sample sizes (165 for Paroxysmal AF and 150 for Persistent AF) are higher than the sample size of 138 for the safety objective. Therefore, a total of 315 Primary Analysis Cohort subjects are needed to have adequate power.

Overall, up to 475 subjects will be enrolled to ensure there are 20 Pilot Phase subjects, up to 80 Pivotal Phase roll-in subjects, and 315 Pivotal Phase primary analysis subjects treated with the PFA system, and to account for subjects not treated prior to exit.

12.3. Secondary Objective

The secondary objective will be evaluated to gain additional information about the performance of the PFA system. The secondary objective will be reported separately by paroxysmal AF and persistent AF.

Within each arm, testing for the two QOL hypothesis tests will be performed if the primary effectiveness and primary safety objectives are met. A Hochberg multiple testing procedure will be utilized to maintain an overall type I error rate of 0.025.

The Hochberg procedure is a stepwise procedure and will be implemented as follows:

The two null hypotheses will be defined as H(1) (AFEQT) and H(2) (EQ-5D). For each of the hypotheses, p-values will be calculated and sorted $p(1) < p(2)$. The decision rule to accept or reject each hypothesis will follow the step-up algorithm, where $\alpha=0.025$:

Step 1: If $p(2) \geq \alpha$, accept H(2) and go to Step 2, otherwise reject both hypotheses and stop

Step 2: If $p(1) < \alpha / 2$ reject H(1); otherwise accept H(1)

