12.3.1.2. EQ-5D Questionnaire

Hypothesis

The following hypothesis will be tested:

$$H_0: \Delta EQ-5D = 0$$

$$H_a: \Delta EQ-5D > 0$$

Where $\Delta EQ-5D$ is the change in mean composite EQ-5D score from baseline to 12 months.

Endpoint Definition

The Euroqol EQ-5D questionnaire (5L version) will be utilized for this objective. The EQ-5D questionnaire is a standardized instrument for measuring generic health status. The EQ-5D has two sections. The first section is a descriptive section where the subject checks a box by the most appropriate statement. The second section is a visual analog scale. Composite scores will be indexed against a US reference population. (Shaw, Johnson and Coons 2004).

The endpoint for each subject is change in EQ-5D composite score, which is the EQ-5D composite score at 12 months minus the EQ-5D composite score at baseline.

Analysis Methods

The mean change in EQ-5D composite score and a two-sided 95% confidence interval will be calculated based on the t-distribution.

█ The p-value based on the final dataset will be compared to the Hochberg alpha level (Section 12.3) to determine significance.

Summary statistics (e.g. mean, SD) will be used to summarize the change in EQ-5D composite scores from baseline through 12 months, including values collected at 6 months. In addition, the visual analog scale of the EQ-5D will be summarized through 12 months using summary statistics.

Performance criteria

If the p-value from the one-sample t-test is less than the Hochberg-criteria alpha level, then the objective will be considered met.

Determination of Subjects/Data for Analysis

Primary Analysis Cohort subjects who have completed baseline and 12-month follow-up questionnaires will be included.

[Redacted text block]

[Redacted text block]

[Redacted text block]

- [Redacted list item]
- [Redacted list item]

[Redacted text block]

[Redacted text block]

[Redacted text block]

[Redacted text block]

[Redacted text block]

[Redacted text block]

[REDACTED]

[REDACTED]

- [REDACTED]
- [REDACTED]
- [REDACTED]

[REDACTED]

[REDACTED]

[REDACTED]

[REDACTED]

[Redacted text block containing multiple lines of blacked-out content]

[Redacted text block containing multiple lines of blacked-out content]

[Redacted text block]

[Redacted text block]

[Redacted text block]

[Redacted text block]

[Redacted text block]

[Redacted text block]

[Redacted text block]

[Redacted text block]

[Redacted text block]

[Redacted text block]

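### The written Hochberg steps in Section 12.3 fix the hypothesis labels by instrument but sort the p-values by size, so they reverse the two quality-of-life decisions in one region

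*Combined protocol and SAP*

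**What the plan says.** Section 12.3 (Secondary Objective) of the combined protocol and SAP covers two quality-of-life tests in each arm, AFEQT and EQ-5D. On the method: "A Hochberg multiple testing procedure will be utilized to maintain an overall type I error rate of 0.025". On the mechanics: "The Hochberg procedure is a stepwise procedure and will be implemented as follows".

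The labels come first: "The two null hypotheses will be defined as H(1) (AFEQT) and H(2) (EQ-5D". The ordering comes next: "For each of the hypotheses, p-values will be calculated and sorted", with p(1) the smaller and p(2) the larger. Two steps follow, with alpha = 0.025:

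- Step 1, if p(2) is at least alpha: "accept H(2) and go to Step 2, otherwise reject both hypotheses and stop".
- Step 2, if p(1) is below alpha/2: "reject H(1); otherwise accept H(1".

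The tests are gated within each arm: "testing for the two QOL hypothesis tests will be performed if the primary effectiveness and primary safety objectives are met".

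Section 12.3.1.2 (EQ-5D Questionnaire) adds: "The p-value based on the final dataset will be compared to the Hochberg alpha level (Section 12.3) to determine significance". Its performance criterion likewise judges EQ-5D on its own t-test p-value. Section 12.3.1.1 (AFEQT) appears in the table of contents, but its text is not in the public document. It could not be checked, and nothing is held against the plan for that.

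**The concern.** In Hochberg's procedure the hypotheses are re-indexed with their p-values, so H(1) is whichever null produced the smaller p-value. Section 12.3 ties H(1) to AFEQT and H(2) to EQ-5D before sorting and never releases them. Step 1 can then accept only EQ-5D, and Step 2 can decide only AFEQT, whichever instrument gave the smaller p-value. A strong EQ-5D result could be credited to AFEQT.

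These steps are the stated implementation, and they decide which quality-of-life objective is declared met in each arm. If they do not return Hochberg's decisions, the promised error rate of 0.025 does not hold in every configuration. There could also be a dispute after the data are seen about which rule was pre-specified.

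**Working it through.** **Inputs.** From Section 12.3: alpha = 0.025, alpha/2 = 0.0125, the fixed labels, the sorting and the two steps. EQ-5D is tested one-sided (Section 12.3.1.2). Powers and correlations are assumptions, because the documents give none for quality of life. Write pA for the AFEQT p-value and pE for the EQ-5D p-value.

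**The plan's own figure.** Under standard Hochberg with both nulls true and independent p-values, P(any rejection) = alpha² + 2 × (alpha/2) × (1 − alpha) = 0.000625 + 0.024375 = 0.025. This reproduces the stated rate.

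**The two rules side by side.**

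| Region | Standard Hochberg | Steps as written |
|---|---|---|
| Both p < 0.025 | reject both | reject both |
| pA < 0.0125, pE ≥ 0.025 | reject AFEQT only | reject AFEQT only |
| pE < 0.0125, pA ≥ 0.025 | reject EQ-5D only | reject AFEQT only |
| Larger p ≥ 0.025, smaller p ≥ 0.0125 | reject neither | reject neither |

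On a grid of 57,600 pairs (each p from 0.0005 to 0.06025 in steps of 0.00025) the decisions differ exactly in the third row, with no exceptions. Under the written steps, EQ-5D can never be rejected alone, and AFEQT is rejected whenever anything is.

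**How often the rules differ.** The rates use bivariate normal test statistics with mean 1.96 + z(power). At correlation 0 the probability is P(pE < 0.0125) × P(pA ≥ 0.025). An EQ-5D test with 50/80/90% power at 0.025 has probability 0.3892/0.7123/0.8414 of falling below 0.0125.

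*Both effective, EQ-5D at 90% power.* At correlation 0: 0.8414 × 0.10 = 8.41% with AFEQT at 90%, and 0.8414 × 0.01 = 0.84% with AFEQT at 99%. Across correlations:

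| AFEQT power | 0 | 0.3 | 0.5 | 0.8 |
|---|---|---|---|---|
| 90% | 8.41% | 6.89% | 5.56% | 2.81% |
| 95% | 4.21% | 3.27% | 2.43% | 0.82% |
| 99% | 0.84% | 0.58% | 0.35% | 0.04% |

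*EQ-5D null, AFEQT power 50/80/90%.* At correlation 0: 0.0125 × 0.5, 0.2 and 0.1 = 0.625%, 0.25% and 0.125%. At 0.3: 0.26%, 0.06% and 0.02%. At 0.5 or more: below 0.1%.

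*AFEQT null, EQ-5D effective (least favourable case).* At correlation 0 and 80% EQ-5D power:

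- Standard Hochberg, false AFEQT rejection: 0.025 × 0.80 + 0.0125 × 0.20 = 0.0225.
- Steps as written: 0.0225 + 0.7123 × 0.975 = 0.0225 + 0.6945 = 0.717.

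Across correlations 0 to 0.8 the written steps give about 39–40%, 71–72% and 84% for EQ-5D power of 50%, 80% and 90%. Standard Hochberg gives 1.9% to 2.5%.

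*Both null.* The chance of any rejection is the same under both rules: 2.50/2.47/2.40/2.19% at correlations 0/0.3/0.5/0.8.

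**Could another reading rescue the text?** Taking p(1) as AFEQT's p-value and p(2) as EQ-5D's, unsorted, contradicts the sorting. It would also reject AFEQT at any p-value once pE < 0.025. With both nulls true and independent, the error becomes 0.025 + 0.975 × 0.0125 = 0.0372, above 0.025.

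**The case against.** The strongest reply is that nobody would program this. The method is named, parenthesised subscripts next to sorted p-values are ordinary order-statistic notation, and letting the EQ-5D p-value reject AFEQT is plainly not meant. Section 12.3.1.2 judges EQ-5D on its own p-value. The Hochberg level can only be 0.025 or 0.0125, so in the disputed region (pE < 0.0125) that section declares EQ-5D met either way. If the unseen Section 12.3.1.1 is written the same way, a false AFEQT claim is blocked too. The 39% to 84% figures also need the AF-specific instrument to be null while the generic one responds, and nothing in the documents suggests that.

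Much of this stands. Standard Hochberg was clearly intended, the least favourable case is unlikely, and the large figures apply only if the steps are followed to the letter and nothing in Section 12.3.1.1 overrides them. But the notation would be ordinary only if the symbols had not been assigned to named questionnaires. Section 12.3.1.2 contradicts the steps in the disputed region without correcting them: it takes its level from Section 12.3 and gives no rule for AFEQT. A reader is left with two answers for EQ-5D and, in the visible text, a wrong one for AFEQT.

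**Conclusion.** The concern holds as a minor error in a stated decision rule. As written, the steps reverse Hochberg if and only if the EQ-5D p-value is below 0.0125 and the AFEQT p-value is at least 0.025; everywhere else the decisions agree. That result is exact and needs no assumption.

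The frequency does rest on assumed powers and correlations, and on literal application. It ranges from 0.04% of trials (AFEQT power 99%, EQ-5D 90%, correlation 0.8) to 8.4% (both 90%, correlation 0) when both instruments respond. It is far higher only if AFEQT is null and EQ-5D is not. The effect is confined to secondary tests that run only after both primary objectives in the arm are met. No primary result, alpha, sample size or power figure changes.

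**What to change.** Remove the fixed instrument labels from Section 12.3 and tie the hypotheses to the ordered p-values, for example:

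> Let p(1) ≤ p(2) be the ordered p-values and H(1), H(2) the null hypotheses corresponding to them. If p(2) < 0.025, reject both. Otherwise accept H(2), and reject H(1) if p(1) < 0.0125.

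The ≤ sign also covers ties, which the strict inequality leaves undefined. Check that the AFEQT criterion in Section 12.3.1.1 uses AFEQT's own p-value, as Section 12.3.1.2 does for EQ-5D.

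The cost is one sentence, in the protocol or in the statistical analysis plan that Section 5.3 says will be written before the data are analysed. Data collection and sample size are unaffected.

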12.3.1. Secondary Objective: Quality of Life

Assess changes in quality of life from baseline through 12 months after the index ablation procedure

This objective has two parts, the AFEQT questionnaire, and the EQ-5D questionnaire.

Additional Analyses

The AFEQT questionnaire has three subscale scores, Daily Activities Subscale, Treatment Concern, and Treatment satisfaction. Each subscale ranges from 0 – 100, where 0 corresponds to low quality-of-life and 100 corresponds to high quality of life. An additional analysis will be conducted to summarize these subscales through 12 months.

Change in AFEQT subscale score is defined as 12-month AFEQT subscale score minus baseline AFEQT subscale score. A two-sided 95% confidence interval will be calculated based on the t-distribution.

12.3.1.2. EQ-5D Questionnaire

Hypothesis

The following hypothesis will be tested:

$$H_0: \Delta EQ-5D = 0$$

$$H_a: \Delta EQ-5D > 0$$

Where $\Delta EQ-5D$ is the change in mean composite EQ-5D score from baseline to 12 months.

Endpoint Definition

The Euroqol EQ-5D questionnaire (5L version) will be utilized for this objective. The EQ-5D questionnaire is a standardized instrument for measuring generic health status. The EQ-5D has two sections. The first section is a descriptive section where the subject checks a box by the most appropriate statement. The second section is a visual analog scale. Composite scores will be indexed against a US reference population. (Shaw, Johnson and Coons 2004).

The endpoint for each subject is change in EQ-5D composite score, which is the EQ-5D composite score at 12 months minus the EQ-5D composite score at baseline.

Analysis Methods

The mean change in EQ-5D composite score and a two-sided 95% confidence interval will be calculated based on the t-distribution.

█ The p-value based on the final dataset will be compared to the Hochberg alpha level (Section 12.3) to determine significance.

Summary statistics (e.g. mean, SD) will be used to summarize the change in EQ-5D composite scores from baseline through 12 months, including values collected at 6 months. In addition, the visual analog scale of the EQ-5D will be summarized through 12 months using summary statistics.

Performance criteria

If the p-value from the one-sample t-test is less than the Hochberg-criteria alpha level, then the objective will be considered met.

Determination of Subjects/Data for Analysis

Primary Analysis Cohort subjects who have completed baseline and 12-month follow-up questionnaires will be included.

[Redacted text block]

[Redacted text block]

[Redacted text block]

- [Redacted list item]
- [Redacted list item]

[Redacted text block]

[Redacted text block]

[Redacted text block]

[Redacted text block]

[Redacted text block]

[Redacted text block]

[REDACTED]

[REDACTED]

- [REDACTED]
- [REDACTED]
- [REDACTED]

[REDACTED]

[REDACTED]

[REDACTED]

[REDACTED]

[Redacted text block containing multiple lines of blacked-out content]

[Redacted text block containing multiple lines of blacked-out content]

[Redacted text block]

[Redacted text block]

[Redacted text block]

[Redacted text block]

[Redacted text block]

[Redacted text block]

[Redacted text block]

[Redacted text block]

[Redacted text block]

[Redacted text block]

[Redacted text block]

[Redacted text block]

[Redacted text block]

[Redacted text block]

[Redacted text block]

[Redacted text block]

[Redacted text block]

[Redacted text block]

[Redacted text block]

[Redacted text block]

[Redacted text block]

13. Ethics

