For every treated subject, day 0 is defined as the day of the index ablation procedure. For subjects with treatment failure, the survival date will be set to the date of the treatment failure. For subjects without treatment failure through 12 months, those subjects will be censored at the last study contact date recorded on a CRF which may include the last study visit, the last weekly patient activated ambulatory, the exit date, or death date. If a subject without a treatment failure is lost to follow-up, the censoring date will be set to the last known study visit date.

For the component of the endpoint, documented AF/AT/AFL, if this documentation resulted from rhythm monitoring occurring at the 12-month visit within the 12-month visit window, the date of recurrence will be set to 365 days from the study ablation procedure so that these events will be counted as treatment failures in the 12-month Kaplan-Meier analysis.

Sensitivity Analyses

A sensitivity analysis will be conducted to estimate the potential impact of subjects with less than 12 months of follow-up at the final analysis. The mortality rate in this patient population is anticipated to be low. The total assumed attrition rate through one year is 5%. Because the primary endpoint will be tested using survival methods, all treated subjects are included in the primary analysis, and therefore no subjects will have complete missing data. For subjects that exit early, a tipping point analysis will be conducted to estimate the potential impact of subjects with less than 12 months of follow-up. These subjects will be defined as subjects with partial data. The tipping point analysis methods will be as follows. For each subject with less than 12 months of follow-up, each subject will be set to treatment failure (failure date set to date of study exit). The 12-month Kaplan-Meier estimate will be re-calculated with the earliest (closest to index ablation) sequentially added to the Kaplan-Meier analysis, and the results presented in table format. The tipping point will be defined as the number of additional failures in which the performance goal (55% for paroxysmal and 40% for persistent) is crossed by the lower 95% confidence bound.

Performance Requirements

If the lower bound of the confidence interval (coverage level determined by the alpha spending function) is greater than the performance goal (55% for paroxysmal and 40% for persistent), the objective will be considered met.

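### The secondary EQ-5D test drops everyone without a 12-month form and leaves the 6-month scores out of the test; if those subjects changed for the worse, its 2.5% error rate rises to about 3.5–6% at the planned 5% attrition

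*Combined protocol and SAP*

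**What the plan says.** All references are to the combined protocol and SAP.

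- **Status of the test.** EQ-5D is one of two quality-of-life hypotheses in each arm. Section 12.3: "A Hochberg multiple testing procedure will be utilized to maintain an overall type I error rate of 0.025". The gate is that "testing for the two QOL hypothesis tests will be performed if the primary effectiveness and primary safety objectives are met".
- **Endpoint and test.** Section 12.3.1.2 takes the change in composite score, "which is the EQ-5D composite score at 12 months minus the EQ-5D composite score at baseline", with a null of zero against a positive change. The success rule is: "If the p-value from the one-sample t-test is less than the Hochberg-criteria alpha level, then the objective will be considered met".
- **Analysis set.** "Primary Analysis Cohort subjects who have completed baseline and 12-month follow-up questionnaires will be included".
- **The 6-month scores.** Table 7 and section 8.9.3 schedule EQ-5D at 6 months. Section 12.3.1.2 uses those values only in summary statistics of "the change in EQ-5D composite scores from baseline through 12 months, including values collected at 6 months".
- **Attrition.** Section 12.2.3: "The total assumed attrition rate through one year is 5" percent. The sample-size assumptions there spread exits uniformly over days 1 to 364.
- **Missing data elsewhere.** Section 12.2.3 keeps all treated subjects in the primary effectiveness analysis and adds a tipping-point analysis for those with under 12 months of follow-up. No counterpart for EQ-5D is visible. The unscheduled visit attempted at early exit (section 8.10) does not list EQ-5D.

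**The concern.** A completers-only mean is unbiased for the whole cohort only if the absence of a 12-month form is unrelated to the change in quality of life. Subjects who had gained little by 6 months are plausible non-completers, and their baseline scores, often with 6-month scores, would be in hand but unused by the test. The study is single-arm and the null is exactly zero, so no control group can cancel such a bias. At stake is a confirmatory secondary claim of improved generic health status whose true error rate would be above the stated 0.025.

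**Working it through.** **1. The plan's own figure.** With a = 0.025 and two independent true nulls, Hochberg rejects at least one with probability P(both p < a) + P(smaller p < a/2 and larger p ≥ a) = a² + 2(a/2)(1 − a) = a = 0.025. Simulation gives 0.0250, 0.0240 and 0.0216 at correlations 0, 0.5 and 0.8. The stated error rate is right when each test is unbiased. What follows concerns bias in one of the two tests.

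**2. Inputs from the documents.** N = 165 (paroxysmal) and 150 (persistent); attrition 5%. Completers: 165 × 0.95 ≈ 157 and 150 × 0.95 ≈ 142. The 6-month window opens on day 183 (Table 8), so under uniform exits about 182/364 = half of leavers go before a 6-month form is due.

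**3. Inputs assumed, because the documents give none.** The gap in 12-month change between completers and leavers (in SD of change), the 6- to 12-month correlation, the missingness mechanism, and any missing fraction above 5%.

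**4. Analytic check.** Let f be the missing fraction and g the gap. Overstatement of the mean change = f × g. If the true mean change over all subjects is zero, the t-test on m completers has non-centrality f × g × √m. For f = 0.05, g = 0.5, m = 157: 0.025 × √157 = 0.313, and P(Z > 1.96 − 0.313) ≈ 5.0%. The exact non-central t results at one-sided 0.025 are:

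| Missing | Gap 0.25 SD (n=165 / 150) | Gap 0.5 SD | Gap 1.0 SD |
|---|---|---|---|
| 5% | 3.6 / 3.5% | 5.0 / 4.8% | 9.1 / 8.6% |
| 10% | 4.9 / 4.7% | 8.8 / 8.3% | 22.6 / 21.0% |

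The 0.025 level applies when the AFEQT p-value is also below 0.025. Otherwise EQ-5D is tested at 0.0125, and the 5% row becomes 1.9 / 1.8%, 2.7 / 2.6% and 5.3 / 4.9%.

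**5. Simulation of the mechanism.** True change zero; logistic missingness on the 6-month change with slope 1 (odds ratio e per SD); correlation 0.5–0.7; both arm sizes.

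- All 5% missing depend on the 6-month change: rejection 4.7–5.9%.
- Half of the 5% leave before 6 months, unrelated to outcome, and half depend on the 6-month change: 3.5–4.1%, with bias 0.013–0.017 SD.
- A regression that uses the 6-month score gives 2.4–2.8% in these 5% settings.
- At 10% missing, all dependent on the 6-month change: about 7–13%.
- Missingness unrelated to outcome: about 2.5%.

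**6. Limit of the remedy.** If exits at 5% depend on the unseen 12-month change (moderate to strong selection), completers give 8.0–17.9% and the analysis using 6-month scores still gives 6.5–13.5%.

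**The case against.** The strongest reply is that the design works against the mechanism. Treatment failure is not a listed reason for exit (section 8.19). Subjects with a repeat ablation stay on the original schedule (section 8.7), and late visits are analysed rather than discarded (section 8.9). Failing subjects therefore remain due for a 12-month form. The test is also secondary and is reached only after both primary objectives are met. Away from the null the effect is small: with 5% missing, correlation 0.6 and n = 165, rejection at a true change of 0.2 SD moves from 72% to 77%, and at 0.3 SD it stays at 97%. Finally, text next to the EQ-5D analysis is redacted and the AFEQT test section is not visible, so a missing-data analysis there cannot be excluded.

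Most of this stands as a limit on size and certainty. It does not remove the point. The gate gives no protection when the device meets its primary objectives and EQ-5D does not change. The visible analysis set and test are explicit.

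Some stronger readings are tempting, and the documents do not support them:

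- **That the mean change is biased upward as a matter of fact.** The documents say nothing about who fails to return forms. What matters is a worse change; losing subjects who merely start lower could even understate it.
- **That the error rate is in the range of 7–13% or more.** With this mechanism that takes about 10% missing, twice the stated attrition. Larger figures at 5% need a gap near 1 SD or strong selection on the unseen score, for which there is no evidence.
- **That the 6-month scores are ignored.** They are summarised; they are absent from the test only.
- **That a mixed model removes the bias.** It does so only where missingness is explained by scores already observed.

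**Conclusion.** The point holds in conditional form. If subjects missing the 12-month form had a worse change from baseline, the completers' t-test overstates the change. At 5% attrition its one-sided error rate is about 3.5–6% instead of 2.5%. That range assumes selection on the 6-month change at an odds ratio of e per SD and a correlation of 0.5–0.7. Its lower end is the case closest to the plan's uniform attrition, with the early half of exits unrelated to outcome. Under this mechanism the rate goes higher only if unreturned forms push missingness above 5%. The 5% describes study exit, and no form-completion rate is given. The SD gap, correlation and non-return rate are assumptions, and the direction is plausible but not shown. Both primary objectives are untouched. The point is worth acting on because a better analysis of data already scheduled costs almost nothing.

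**What to change.** In section 12.3.1.2:

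1. Make the tested quantity the 12-month change from a repeated-measures model with baseline, 6- and 12-month scores, in all Primary Analysis Cohort subjects with a baseline form.
2. Keep the completers' one-sample t-test as a sensitivity analysis.
3. Add a delta-adjusted or tipping-point sensitivity analysis, modelled on the one in section 12.2.3. The model does not correct missingness that depends on the unseen 12-month score, nor selective exits before 6 months. When about half of leavers have no 6-month score and exits are selective throughout, using the available 6-month scores lowers rejection at 5% missing from 4.4–6.4% to 3.0–4.4%, which is better but not fully restored.

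Cost: SAP wording, a few lines of code and slightly more complex reporting. No new data are needed. If the redacted text already holds such an analysis, only the choice of the tested analysis remains to be changed.
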